8.3 Required Reporting: Affiliates to the Masonic Cancer Center

Beginning with the signing of the consent and continuing through the final treatment visit, affiliate institutions will report all events meeting the definition of serious, regardless of attribution or expectedness, within 24 hours of knowledge of the event to the University of Minnesota Study Coordinator. After the final treatment visit, the investigator is obligated, upon knowledge of, to report any event that meets the definition of serious or life-threatening and is felt to be at least possibly related to the study drugs.

Reports are to be submitted to the Study Coordinator at the University of Minnesota Masonic Cancer Center (MCC) using the SAE reporting form found OnCore. The MCC Study Coordinator will facilitate reporting to the University Of Minnesota IRB and the FDA as required.

Affiliate institutions will be responsible for submitting reportable events to their institutional IRB and any other required local regulatory entities.

8.4 U of MN Required Reporting: FDA, IRB, MCC's SAE Coordinator, NewLink and Dendreon

The reporting period for this study is from initiation of any study treatment through the final treatment visit approximately 30 days after the last dose of indoximod/placebo; however after this point, the investigator must report upon knowledge any study treatment related event meeting the expedited reporting criteria below.

Agency	Criteria for reporting	Timeframe	Form to Use	Submission address/ fax numbers	Copy to:
U of MN IRB	Events requiring prompt reporting including, but not limited to unanticipated death of a locally enrolled subject(s); new or increased risk; any adverse event that require a change to the protocol or consent form or any protocol deviation that resulting in harm refer to http://www.research.umn.edu/irb/guidance/ae.html#.VC7xral0-sh	within 5 business days of discovery	Report Form	[contact]	MCC SAE Coordinator [contact]
FDA	Unexpected and fatal or life threatening suspected adverse reaction	As soon as possible but no later than 7 Calendar-Day	UMCC SAE	Submit as an amendment to IND with a copy to all participating affiliate institutions, Dendreon, and NewLink	
1) Serious and unexpected suspected adverse reaction or 2) increased occurrence of serious suspected adverse reactions over that listed in the protocol or investigator brochure or 3) findings from other sources (other studies, animal or in vitro testing)	As soon as possible but no later than 15 Calendar-Day				
	All other events per CFR 312.33	At time of FDA annual report	Summary format	Submit as an amendment to IND	Not applicable
Note: Events due to the disease under treatment or an underlying medical condition will not require expedited reporting to the FDA for the purposes of this study					
Dendreon and NewLink (see details next page)	All SAEs that occur from the signing of the Study-specific consent through the duration of the post-therapy adverse event collection period (final treatment visit)	24 hours of awareness of event	UMCC SAE	Dendreon Corporation Attn: Safety Manager [contact] [contact] After Hours: [contact] NewLink Genetics Attn: Safety Manager [contact] [contact] [name] After Hours: [contact] Email: [contact] with a copy to all participating affiliate institutions	SAE Coordinator [contact]

Masonic Cancer Center SAE Coordinator	Early stopping rule event per section 12.2	Upon reporting	Early stopping rule form	SAE Coordinator [contact]	Not applicable
--	---	----------------	--------------------------------	-------------------------------------	----------------

In each IND safety report, the sponsor must identify all IND safety reports previously submitted to the FDA concerning a similar suspected adverse reaction and must analyze the significance of the suspected adverse reaction in light of the previous, similar reports.

The SAE Coordinator will provide the Masonic Cancer Center's Data and Safety Monitoring Council (DSMC) with the SAE in an appropriate format depending on the individual SAE (as reported or in a summary format).

Dendreon and NewLink Serious Event Reporting

Sponsor shall notify institution, investigator and IRB immediately during the conduct of the study and/or after the study is completed should it become aware of information related to the study that would impact participant safety or clinical care. Institution shall promptly disclose such information to study participants.

Significant new information regarding an ongoing SAE and the resolution must be sent to Dendreon and NewLinks within 3 business days of awareness of the new information.

9 Measurement of Effect

9.1 Immune Response to PA2024

The frequency of antigen specific, cytokine producing cells will be determined by an ELISPOT assay. ELISPOT assay will use whole PBMC to assess interferon gamma production in response to the immunizing protein PA2024. Increase in number of ELISPOT responses to PBMC in patients in the treatment arm will be compared to those in control arm.

9.2 Progression Free Survival

Progression free survival (PFS) is a composite endpoint defined as disease progression in bone or soft tissues, PSA progression, worsening pain, or death. PFS will be measured in months from the time of study enrollment until the date disease progression. During the first 12 weeks PSA progression alone will not be used as the sole criterion for clinical decision making to determine disease progression as per recommendations from Prostate Cancer Working Group -2 (PCWG2)(10).

9.3 PSA Progression

PSA measurements obtained during the first 12 weeks of indoximod/placebo will not be used as the sole criterion for establishing disease progression. Treatment will be discontinued if rapid disease progression is documented or the patient develops worsening symptoms of disease or toxicity. PSA progression is defined as the first PSA value that shows $\geq 25\%$ increase from baseline and has a minimum absolute increase of ≥ 2 ng/mL after 12 weeks of treatment.

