5.2.1 Expected Side Effects

All of the subjects in the indoximod clinical trials had at least one adverse event. The most frequently reported adverse events (regardless of attribution), occurring in $\geq 20\%$ of patients were fatigue, nausea, headache, and alopecia. The most frequently reported laboratory abnormalities (regardless of attribution), occurring in $\geq 20\%$ of patients were lymphopenia, anemia and hyperglycemia.

The most frequently observed adverse event which is possibly related to indoximod is fatigue (12%). Lymphopenia (16%) is the most frequently observed laboratory abnormality possibly related to

indoximod. The collective safety data from the clinical studies so far indicates indoximod has an acceptable safety profile and is safe for the treatment of patients with solid tumors.

Toxicities as updated with version 6 of the indoximod investigator's brochure (February 2015) are as follows:

Likely: Likely to happen to 20% or more of patients

- Fatigue or feeling tired
- Nausea
- Anorexia or loss of appetite
- Decrease in red blood cells (anemia)
- Diarrhea

Less Likely: Likely to happen to 10 to 19% of patients

- Decrease in white blood cells (neutrophils and lymphocytes)
- Abdominal pain
- Feeling short of breath or breathless (dyspnea)
- Rash
- Vomiting
- Constipation
- Decrease in platelets
- Headache
- Hair loss

Rare: Likely to happen to 1% than 10% of patients

- Dizziness
- Fever associated with low white blood cells
- Lung infection
- Increase in blood potassium, glucose, and creatinine levels
- Sleeplessness (insomnia)
- Low blood levels of sodium
- Multi-organ failure
- Low blood pressure
- Dehydration
- Ringing in ears
- Fever associated with low white blood cells (febrile neutropenia)
- Mouth Sores (Oral mucositis)
- Decrease in white blood cells

This drug is being employed in human clinical trials for solid tumors, breast cancer, melanoma, and pancreatic cancer. The profile of adverse events appears similar to that predicted for the study

subjects enrolled in these studies, e.g., a patient population with life-threatening disease. (7).

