The data obtained from the Phase 1 studies performed under IND78060 suggest that certain patients with a history of exposure to targeted biologics involving components of the IDO pathway may be adversely impacted following administration of indoximod. However, these same patients were observed to have a clinical response after management of the toxicity. Therefore, the combination of indoximod with biologic agents including ipilimumab is being carefully evaluated in the clinical trial setting as described above.

The drug has not shown evidence of significant drug interactions. It is now being systematically tested in combination with docetaxel for metastatic breast cancer, in combination with ipilimumab for metastatic melanoma, in combination with temozolomide for glioblastoma, and in combination with gemcitabine/nabpaclitaxel for metastatic pancreas cancer in clinical trials under IND78189 and IND120813.

Based on phase I testing no serious toxicity is anticipated. Therefore, no specific supportive care measures are expected to be required for the drug administration itself; however dose withholding will occur for Grade 3 and 4 treatment related toxicity per section 5.2.3. Unexpected adverse events will be treated as medically indicated by the involved physicians.

Specific attention to development of autoimmune events or activation of latent infections will be given as trials using other immune-modulatory agents such as CTLA-4 blocking antibodies have shown a correlation between disease responses and so called autoimmune breakthrough events (ABEs) like hypophysitis, colitis, autoimmune hepatitis, or dermatitis. It is for this reason that they are distinguished from other adverse events. When used immediately post sipuleucel-T as in this clinical trial, it might increase the side effects of cytokine release from last infusion of sipuleucel-T. Refer to section 6.2 for study specific monitoring. Section 5.2.2 provides management of selected events.

Placebo

Placebo is a look-alike capsule containing no active ingredients and therefore no serious side effects are expected.

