5.2.3 Indoximod /Placebo Dose Modifications (toxicity related)

Should a patient experience a Grade 3 toxicity that is possibly, probably, or definitely related to the study drug as determined by the treating investigator, the study drug will be held.

- If the toxicity resolves to Grade 2 or less within 7 days, the study drug may be resumed. If the toxicity recurs the event will count toward the early study stopping rule for excessive toxicity (section 12.2).
- If the toxicity does not improve to a grade 2 or less within 7 days or recurs, the patient will be permanently discontinued from treatment and the event will count toward the early study stopping rule for excessive toxicity (section 12.2).

If the patient experiences any Grade 4 toxicity, the study drug will be stopped and the event will count toward the early study stopping rule for excessive toxicity (section 12.2). If all toxicities resolved to Grade 2 or less, resumption of the study drug may be considered but must be discussed and agreed to by the investigator and Principal Investigator ([name]).

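### Section 9.3 stops study drug for worsening toxicity without grade or attribution, at odds with the graded rule in 5.2.3, and Grade 4 attribution is unclear across 5.2.1, 5.2.3, 8.2 and 12.2

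*Combined protocol and SAP*

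**What the plan says.** The operative rule is in section 5.2.3. Its Grade 3 limb is conditional on attribution: "Should a patient experience a Grade 3 toxicity that is possibly, probably, or definitely related to the study drug" leads to a hold. Then "If the toxicity resolves to Grade 2 or less within 7 days, the study drug may be resumed"; otherwise, "If the toxicity does not improve to a grade 2 or less within 7 days or recurs, the patient will be permanently discontinued". Its Grade 4 limb has no such condition: "If the patient experiences any Grade 4 toxicity, the study drug will be stopped". The event then counts toward the early stopping rule, and once toxicities have settled, "resumption of the study drug may be considered but must be discussed and agreed to by the investigator" and the Principal Investigator.

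Section 5.2.1 summarises this by cross-reference: "dose withholding will occur for Grade 3 and 4 treatment related toxicity per section 5.2.3".

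Section 9.3 defines PSA progression. After saying that PSA alone does not establish progression in the first 12 weeks of study drug, it adds: "Treatment will be discontinued if rapid disease progression is documented or the patient develops worsening symptoms of disease or toxicity".

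Three other sections bear on the point:

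- **5.4** lists reasons to end treatment, including unacceptable adverse events and an investigator's judgement of the patient's best interest. Neither is tied to a grade.
- **8.2** marks with an asterisk the events that count toward early termination. The asterisk is on the possible/probable/definite row only, but its footnote covers all Grade 4 and 5 events.
- **12.2** defines excess toxicity as unresolved treatment-related Grade 3 events plus any Grade 4 or 5 event.

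**The concern.** A site that looks up what to do about toxicity can find two instructions. The one in 9.3 is mandatory in form and turns on the word worsening, without grade or causality. The one in 5.2.3 is graded, partly conditional on causality, and has a hold-and-restart step. The two sections do not refer to each other.

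Up to 5 sites randomise and treat locally, so men with the same event could be managed differently. The exposure at stake includes the period that matters for the primary endpoint. Study drug starts in week 4 and the ELISPOT sample is at week 14, so there are 14 - 4 = 10 weeks of dosing before it. All of these fall inside the 12-week window that 9.3 is discussing.

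The Grade 4 ambiguity also reaches the safety monitoring. 5.2.3, 8.2 and 12.2 all feed the early stopping rule, so whether an unrelated Grade 4 event counts is a question about the trial's stopping boundary as well as one man's dosing.

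**Working it through.** The plan states no figure on this point, so there is none to reproduce. The check sets the sections side by side, event by event.

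| Event | 5.2.1 (defers to 5.2.3) | 5.2.3 | 9.3 read literally |
|---|---|---|---|
| Toxicity worsening within Grades 1-2 | No withholding described | No action specified | Discontinue |
| Related Grade 3, down to Grade 2 or lower within 7 days | Withhold | Hold, may restart | Discontinue; no restart step |
| Related Grade 3, persisting or recurring | Withhold | Permanent discontinuation | Discontinue |
| Related Grade 4 | Withhold | Stop; restart possible by agreement | Discontinue; no restart step |
| Grade 4 judged unrelated | Not among the events described | Stop, if *any* is taken at face value; restart possible by agreement | Discontinue |

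**Step 1: 9.3 against 5.2.3.** In the third row both sections end treatment. In the first two rows they differ. In the first, 5.2.3 leaves the man on drug unless another provision applies, while 9.3 discontinues. In the second, 5.2.3 provides a route back to treatment and 9.3 mentions none.

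**Step 2: Grade 4 attribution.** Four texts are relevant:

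- 5.2.1 describes 5.2.3 as dealing with treatment-related Grade 3 and 4.
- 5.2.3 attaches a causality condition to Grade 3 and drops it for Grade 4.
- 12.2 makes the same contrast: related for Grade 3, any for Grades 4 and 5.
- 8.2 points both ways. Its footnote repeats the contrast in 12.2, but in the table an unrelated Grade 4 or 5 event must be documented and carries no asterisk.

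The contrast in 5.2.3 and 12.2 favours reading *any* as including unrelated events. The table in 8.2 and the summary in 5.2.1 favour restricting it to related ones. The text does not settle the matter.

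**Step 3: consequence for the stopping rule.** The limits in 12.2 are 3 events in the first 5 subjects, 4 in the first 15, or 5 at any point. One event admitted or left out is therefore 1/3, 1/4 or 1/5 of the relevant limit.

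**Step 4: consequence for the week-14 data.** The week-14 immune sample is in the during-treatment schedule (6.2). The baseline and post-treatment schedule (6.1) marks immune samples at baseline only. The documents do not say whether a man who stopped drug before week 14 still gives that sample. Different stopping practice could therefore affect both exposure and completeness of the primary measurement.

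**Step 5: size.** Putting a number on this needs the rate of worsening toxicity below Grade 3, the rate of rapidly resolving related Grade 3, and the rate of unrelated Grade 4. None is given.

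**The case against.** The strongest reply is that 9.3 is not a dosing section. It sits under measurement of effect, and the sentence follows a caution against acting on early PSA. Its natural job is to say that other reasons for stopping still apply. The section actually titled for toxicity-related dose modification is 5.2.3, and 5.4 governs duration. Clinicians already have discretion below Grade 3: 5.4 allows stopping without a grade, and 5.2.2 provides for holds in autoimmune and pituitary events without a grade threshold. So *no action below Grade 3* describes 5.2.3, not the whole protocol.

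Much of this stands, and it limits the point to a wording inconsistency. It does not remove it. The sentence in 9.3 is mandatory and does not say that it defers to 5.2.3 or 5.4. Worsening is also a different test from the unacceptable events and investigator judgement in 5.4.

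A reader might infer several stronger things that the documents do not support:

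- **That there are three competing rules.** Section 5.2.1 defers to 5.2.3 by name and agrees with it on Grade 3. It does not say that withholding is limited to related events; that is inferred from silence.
- **That 9.3 requires a permanent stop.** The word permanently is not in 9.3. It appears in 5.2.3 for Grade 3, and 5.4 uses discontinuation for an interruption that can be counted in days.
- **That progression follow-up is lost.** Section 5.5 follows every man who begins study drug until progression. At most, scan timing shifts, because 6.1 counts follow-up visits from the post-treatment visit.

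**Conclusion.** The inconsistency is real and can be seen from the text alone. Sections 9.3 and 5.2.3 prescribe different actions for worsening Grade 1-2 toxicity and for a related Grade 3 that resolves quickly. Attribution at Grade 4 is ambiguous, not a proven contradiction, and it affects both dosing and the count toward the early stopping rule. The first conclusion rests on reading the sentence in 9.3 as an instruction, which its wording supports. The second rests on the mismatch among 5.2.1, 5.2.3, 8.2 and 12.2.

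No numerical size should be attached. It is tempting to take the category in 5.2.1, "Likely: Likely to happen to 20% or more of patients", and compute 20% x 25 = 5 men in the indoximod arm stopped under 9.3. That figure is a rate of occurrence, not of worsening, and no placebo rate is given, so it is not a difference between arms. Nor do the documents show a diluted ELISPOT contrast. That would need toxicity to differ by arm and sites to follow 9.3 over 5.2.3, and neither is established. What can be said is that exposure before week 14 may depend on which section a site follows, and that correcting this is cheap.

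**What to change.** Reconcile 5.2.1, 5.2.3, 5.4, 8.2, 9.3 and 12.2:

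- State the toxicity discontinuation rule in one place. In 9.3, either remove the toxicity clause or replace it with a reference to that place, and make clear how the discretionary grounds in 5.4 relate to it.
- State once whether Grade 4 (and, for the stopping rule, Grade 5) events are included regardless of attribution. Carry the same wording into 5.2.1, 5.2.3 and 12.2, and make the asterisks and footnote in 8.2 agree with it.

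Which clinical rule applies, and which attribution is intended, are for the sponsor to decide. The cost is a wording amendment, with any matching change to the early stopping event form. No new visits, procedures or patients are needed.

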We plan to offer trans-rectal biopsy of prostate prior to initiating therapy with sipuleucel-T and at 14 weeks from start of therapy for all patients who have an intact prostate and have not received radiation to the prostate. We will also offer biopsies to patients who have an easily accessible metastasis that can be biopsied before and after treatment. Biopsy of the primary tumor or metastatic site will help understand local immune response to treatment in individual patients. Simultaneous assessment of the immune response within the peripheral blood and within the tumor will help understand immune response to treatment and possibly establish markers of response. The information gained from this study would help devise strategies to better develop sipuleucel-T, indoximod and other immunotherapies for prostate cancer.

3 Patient Selection

Study entry is open to adult men regardless of race or ethnic background. While there will be every effort to seek out and include minority patients, the patient population is expected to be similar to that of other prostate cancer studies at the University Of Minnesota and other participating institutions.

Patients with metastatic castration resistant prostate cancer with minimally symptomatic or asymptomatic disease (the clinical indication for use of sipuleucel-t) will be considered for enrollment in this clinical trial.

Inclusion Criteria

- 3.1** Histologically documented adenocarcinoma of the prostate with metastatic disease as evidenced by soft tissue (e.g. lymphoid) and/or bony metastases on baseline CT scan of the abdomen and pelvis and/or bone scan
- 3.2** Castration-resistant based on a current or historical evidence of disease progression despite surgical or medical castration as demonstrated by one or more of the following:
 - PSA progression (defined as two consecutive PSA measurements at least 14 days apart ≥ 2.0 ng/ml and $\geq 50\%$ above the minimum PSA during castration therapy or above pre-treatment value if no response)
 - progression of measurable disease based on RECIST ($\geq 20\%$ increase in the sum of the diameters of all target lesions or the development of any new lesions – appendix III)
 - progression of non-measurable disease based on imaging studies pre section 9.4
- 3.3** Serum PSA ≥ 2.0 ng/ml at study enrollment
- 3.4** Castration levels of testosterone defined as ≤ 50 ng/dL at study enrollment

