6.1 Baseline and Post Treatment

Study	baseline	Weeks 0-28	Post rx visit	F/U
Evaluation	Prior to 1 st leukapheresis	Refer to table in 6.2	4 weeks after last dose of indoximod /placebo	Every 3 months from post-rx visit until 2 years from enrollment ⁸
Consent	X			
Medical history	X			
Physical exam	X			
Assessment of symptoms and analgesic needs	X		X	X
Weight	X		X	
Vital signs	X		X	
ECOG PS	X		X	
CBC/diff/plt, CD4 count	X		X	
Bun/creatinine, Na, K, Ca, Mg, tot. bili, AST, ALT, alkaline phosphatase, LDH, albumin, total protein	X		X	
Circulating Tumor Cells (CTCs)	X			
PT/INR, CPK	X			
Urinalysis ¹	X			
Testosterone	X		X	
HIV 1 & 2, hepatitis B, Hepatitis C, HTLV-1	X			
β-HCG	X			
ESR	X			
EKG	X			
CT of chest, abd, pelvis	X			X
Bone scan	X			X
PSA	X			X
Research Related				
FACT-P questionnaire	X		X	
TSH, Free T4, LH, FSH, ACTH, Cortisol ⁴	X			
Toxoplasma Ab titer	X		X ⁵	
Rheumatoid Factor	X			
C-Reactive Protein	X			
ANA panel ³ and auto-immune symptom checklist (app IV)	X			
C3, C4, CH50	X			
Samples for immune monitoring, K/T ratio and indoximod level (9 – 10 ml green tops, 1-10 ml red top)	X, X ⁶			
immune response biomarker (1-10 ml red top)	X			
Optional bx ⁷	X			

- 1- Proteinuria – any protein ≥ 2+ on dipstick or new urine active sediment/EOS should be evaluated per section 5.2.2
- 2- Toxoplasma serology positive patients will be offered prophylaxis with Septra DS per section 5.2.2
- 3- Refer to section 5.2.2 for positive ANA panel or symptoms of an autoimmune condition
- 4- Refer to section 5.2.2 for TSH > 5 or evidence of hypopituitarism
- 5- Retest sero-negative patients per section 5.2.2
- 6- Two separate sets of baseline samples to be done (i.e. at screening and prior to 1st sipuleucel-T infusion)
- 7- Biopsy for immune response biomarker only for those who provided additional consent within the treatment consent
- 8- Once disease progression is confirmed follow for survival status only

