6.2 During Treatment

Treatment	Week	Standard of Care			Research funded lab work to be performed by local (institutional) lab	Research Related Samples	indoximod / placebo count
Leukapheresis followed by sipuleucel-T infusion	0						
	1						
Leukapheresis followed by sipuleucel-T infusion	2						
	3						
Leukapheresis followed by sipuleucel-T infusion, start indoximod /placebo day after infusion	4	Prior to indoximod /placebo Physical exam, FACT-P				9 – 10 cc green, 1 – 10 cc red (pre indoximod/ placebo)	
indoximod /placebo twice daily continuously for 6 months	5						
	6	PE, review of side effects		CBC/diff/plt, chem ¹ , U/A ²	Thyroid function, C-reactive protein, ANA panel, Auto-immune symptom list	9 – 10 cc green, 1 – 10 cc red	Reconcile Drug
	7						
	8	PE, review of side effects, FACT-P	PSA	CBC/diff/plt, chem ¹ , U/A ²	Thyroid function, C-reactive protein, ANA panel, Auto-immune symptom list		Reconcile Drug
	9						
	10	PE, review of side effects		CBC/diff/plt, chem ¹ , U/A ²	Thyroid function, C-reactive protein, ANA panel, Auto-immune symptom list	9 – 10 cc green, 1 – 10 cc red	Reconcile Drug
	11-13						
	14	PE, review of side effects, FACT-P	PSA, CT of chest, abd, pelvis, bone scan	CBC/diff/plt, chem ¹ , CTCs ³ , U/A ²	Thyroid function, C-reactive protein, ANA panel, Auto-immune symptom list	9 – 10 cc green, 2 – 10 cc red, opt biopsy	Reconcile Drug
	15-19						
	20	PE, review of side effects, FACT-P	PSA	CBC/diff/plt, chem ¹ , U/A ²	Thyroid function, C-reactive protein, ANA panel, Auto-immune symptom list		Reconcile Drug
	21-23						
	24	PE, review of side effects		CBC/diff/plt, chem ¹ , protein, U/A ²			Reconcile Drug
	25-27						
28	PE, review of side effects, FACT-P	PSA, CT of chest, abd, pelvis, bone scan,	CBC/diff/plt, chem ¹ , U/A ²	Thyroid function, C-reactive protein, ANA panel, Auto-immune symptom list	9 – 10 cc green, 1 – 10 cc red	Final Reconcile Drug	

1- chem to include Bun/creatinine, Na, K, Ca, Mg, tot. bili, AST, ALT, alkaline phosphatase, LDH, albumin, total protein

2- Proteinuria – any protein ≥ 2+ on dipstick or new urine active sediment/EOS should be evaluated per section 5.2.2

3- CTCs - circulating tumor cells

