Partial Response (PR): At least a 30% decrease in the sum of the diameters of target lesions, taking as reference the baseline sum diameters

Progressive Disease (PD): At least a 20% increase in the sum of the diameters of target lesions, taking as reference the smallest sum on study (this includes the baseline sum if that is the smallest on study). In addition to the relative increase of 20%, the sum must also demonstrate an absolute increase of at least

5 mm. (Note: the appearance of one or more new lesions is also considered progressions).

Stable Disease (SD): Neither sufficient shrinkage to qualify for PR nor sufficient increase to qualify for PD, taking as reference the smallest sum diameters while on study.

Evaluation of Non-Target Lesions

Complete Response (CR): Disappearance of all non-target lesions and normalization of tumor marker level. All lymph nodes must be non-pathological in size (<10 mm short axis)

Note: If tumor markers are initially above the upper normal limit, they must normalize for a patient to be considered in complete clinical response.

Non-CR/Non-PD: Persistence of one or more non-target lesion(s) and/or maintenance of tumor marker level above the normal limits

Progressive Disease (PD): Appearance of one or more new lesions and/or *unequivocal progression* of existing non-target lesions. *Unequivocal progression* should not normally trump target lesion status. It must be representative of overall disease status change, not a single lesion increase.

Although a clear progression of “non-target” lesions only is exceptional, the opinion of the treating physician should prevail in such circumstances, and the progression status should be confirmed at a later time by the review panel (or Principal Investigator).

Evaluation of Best Overall Response

The best overall response is the best response recorded from the start of the treatment until disease progression/recurrence (taking as reference for progressive disease the smallest measurements recorded since the treatment started). The patient's best response assignment will depend on the achievement of both measurement and confirmation criteria.

For Patients with Measurable Disease (i.e., Target Disease)

Target Lesions	Non-Target Lesions	New Lesions	Overall Response	Best Overall Response when Confirmation is Required*
CR	CR	No	CR	≥4 wks. Confirmation**
CR	Non-CR/Non-PD	No	PR	≥4 wks. Confirmation**
CR	Not evaluated	No	PR	
PR	Non-CR/Non-PD/not evaluated	No	PR	

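### On-study PSA progression is measured from the enrollment PSA and never from the lowest value on study, so PSA relapse after a fall is dated late in PFS

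*Combined protocol and SAP*

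**What the plan says.** Section 9.2: "Progression free survival (PFS) is a composite endpoint defined as disease progression in bone or soft tissues, PSA progression, worsening pain, or death". The PFS clock starts at study enrollment.

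Section 9.3: "PSA progression is defined as the first PSA value that shows $\geq 25\%$ increase from baseline". The rise must also be at least 2 ng/mL and be seen "after 12 weeks of treatment". The same section adds: "PSA measurements obtained during the first 12 weeks of indoximod/placebo will not be used as the sole criterion for establishing disease progression". It does not define baseline, names no lowest value as reference and asks for no confirmation.

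The table in section 6.1 puts the baseline PSA in the column headed "Prior to 1 st leukapheresis". PSA next appears in that table only in follow-up, every 3 months; none is marked at the post-treatment visit. The table in section 6.2 lists PSA at weeks 8, 14, 20 and 28. The week 4 entry reads "Prior to indoximod /placebo Physical exam, FACT-P" plus research tubes, with no PSA.

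Other progression rules in the same protocol are built differently:

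- Appendix III, soft tissue: "taking as reference the smallest sum on study (this includes the baseline sum if that is the smallest on study").
- Section 3.2, PSA progression for eligibility: "two consecutive PSA measurements at least 14 days apart", judged against the minimum PSA under castration, or the pre-treatment value if there was no response.
- Section 9.4, bone: progression at the first assessment must be confirmed by a later scan.

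**The concern.** The PSA reference is fixed at a value taken before sipuleucel-T. A man whose PSA falls and then climbs must regain all the lost ground and go 25% beyond it before he has a PSA event. His relapse therefore enters PFS late, unless another component occurs first.

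Section 2.2 reports that sipuleucel-T did not improve the rate of PSA declines above 25%, so few falls may be seen on sipuleucel-T alone. The rule then matters most if indoximod lowers PSA. In that case the late dating falls mainly in the indoximod arm and lengthens its PFS.

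A second, smaller matter concerns men whose PSA simply rises. Whatever rise occurs between the enrollment sample and the first dose counts toward the 25%, although study drug could not have influenced it.

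PFS is a secondary endpoint, and sections 1.2 and 12 use it for the efficacy objective on time to progression, through Kaplan-Meier curves and Cox regression.

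**Working it through.** **Plan's own figures.** Section 12 gives no event count, power or hazard ratio for PFS, so there is none to reproduce. The one efficacy design figure, 80% power for ELISPOT with 25 per arm, does reproduce: log SD = √ln(1 + 1.6²) = 1.127, difference = ln 2.5 = 0.916, power 80.4% by the noncentral t. It does not bear on this point.

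**Timeline.**

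- Third leukapheresis on day 28, infusion 3 days later, study drug 1 day after that: 28 + 3 + 1 = day 32, or 4.6 weeks. This is the minimum gap from the baseline PSA to the first dose.
- Week 14 is (98 − 32)/7 = 9.4 weeks on drug; week 20 is (140 − 32)/7 = 15.4 weeks. Reading the 12 weeks as weeks of study drug, week 20 is the first scheduled PSA that can count alone.
- Drug for 24 weeks ends at day 32 + 168 = 200. The post-treatment visit is at day 228. The first follow-up, 3 months (91 days) later, is at day 319, about week 46. From week 28 (day 196) that is 123 days, or 17.6 weeks.

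**Relapse after a fall.** With baseline B of at least 8 ng/mL, 25% is at least 2 ng/mL and the line is 1.25B. After a fractional fall d, the rise needed above the lowest value is 1.25/(1 − d) − 1:

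| Fall from baseline | Rise above lowest value needed under 9.3 |
|---|---|
| 30% | 79% |
| 50% | 150% |
| 80% | 525% |

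The delay against a lowest-value rule is the doubling time × log2(line from baseline / line from lowest value). For 40 falling to 20, the lines are 50 and 25, one doubling apart. That is 3, 6 or 12 months at doubling times of 3, 6 or 12 months (assumed; the documents give none).

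**Worked case.** PSA is 40 at enrollment, 10 at week 14 and 45 at week 28.

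- Under 9.3: 45/40 = 1.125, a rise of 12.5%, so no event. The line is 50. Growth from 10 to 45 is log2(4.5) = 2.17 doublings in 14 weeks, or 6.45 weeks each. At that rate 50 is reached log2(50/45) × 6.45 = 1.0 week after week 28, but the next scheduled PSA is at about week 46.
- From the lowest value: the line is 12.5 (the rise of 2.5 exceeds 2). Week 28 is far above it, so the event is dated no later than week 28, about 18 weeks earlier. If growth was steady from week 14, the week 20 value is 10 × 4.5^(6/14) = 19. It qualifies, and week 28 confirms it. The event is then dated at week 20, about 26 weeks earlier.

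**Rise before study drug.** A 25% rise is log2(1.25) = 0.322 doublings. Over 32 days (1.05 months), the run-in alone gets there if the doubling time is at most 1.05/0.322 = 3.3 months and PSA is at least 8; below 8 the 2 ng/mL condition governs. If the baseline PSA were drawn 14 days earlier (assumed; no PSA window is given), the limit is 4.7 months. Assuming exponential growth:

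| Doubling time (assumed, months) | Rise by day 32 | Share of the 25% line used (log scale) |
|---|---|---|
| 2 | 44.0% | 163% |
| 3 | 27.5% | 109% |
| 4 | 20.0% | 82% |
| 6 | 12.9% | 54% |
| 9 | 8.4% | 36% |
| 12 | 6.3% | 27% |

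**The case against.** A fixed enrollment reference can be defended. It matches the PFS clock in section 9.2, which also starts at enrollment. RECIST and the eligibility rule serve other purposes, so their use of the lowest value is not a contradiction. A man still near his enrollment PSA has arguably kept some benefit. Follow-up PSA, CT and bone scan continue every 3 months, so a relapse is caught later rather than lost. PFS is secondary and has no stated power. All of this stands, and it limits the weight of the point. It does not explain why soft-tissue relapse is dated from the smallest measurement while PSA relapse in the same composite is not, or why bone progression at first assessment needs confirmation and a PSA value never does.

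A reader might infer three stronger things that the documents do not support.

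- **That part of PFS is settled before study drug.** No PSA value counts alone until after 12 weeks of drug, and it must be above the line then. The run-in rise contributes; it reaches 25% by itself only in fast risers.
- **That the run-in rise biases the arms.** Randomization is at week 4 and blinded, so the rise is balanced in expectation. The effect is dilution.
- **That a relapsing man stays progression-free.** He lacks only a PSA event, and only until he passes his enrollment value by 25% and 2 ng/mL. Imaging, worsening pain or death can end his PFS sooner.

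**Conclusion.** The concern holds as a weakness in the definition of a secondary endpoint. Read as written, section 9.3 dates PSA relapse after a fall late: by about 18 to 26 weeks in the worked case, and by one doubling time after a 50% fall from 40 ng/mL, before visit spacing is added. If indoximod lowers PSA, the lateness would favor that arm. The dilution from the pre-drug rise is a secondary point, and its size depends on doubling times that the documents do not give.

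The conclusion rests on taking the enrollment PSA as baseline (the only one scheduled before study drug), on counting the 12 weeks from study drug, and, for week 46, on a man who completes 24 weeks of drug and is seen on schedule. No effect on the PFS hazard ratio can be derived from the documents, because imaging, pain and death also count. The ELISPOT primary analysis is unaffected. The definition should be changed, but the trial's main conclusion does not depend on it.

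**What to change.** For the PFS endpoint definition only, revise section 9.3 to:

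- measure the rise of at least 25% and at least 2 ng/mL from the lowest PSA on study, including baseline, and define baseline as the enrollment PSA;
- keep counting only values after 12 weeks of study drug;
- require the next scheduled PSA to confirm the rise;
- date the event at the first qualifying value.

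This uses PSA values already scheduled. It has two costs. The lowest of several noisy values sits slightly low, which confirmation limits. Confirmation of a week 28 value waits for follow-up PSA at about week 46, although the event keeps its week 28 date.

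The change repairs the relapse problem but not the dilution: in a man whose PSA rises steadily, baseline is already the lowest value. Adding a PSA to the existing week 4 pre-drug draw and using it as the starting reference would address that. It is optional, costs one assay, and makes the reference differ from the enrollment-based PFS clock.

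This is not a proposal to change when treatment stops. Sections 5.4, 9.2 and 9.3 mix endpoint wording with treatment decisions and should be reconciled with the revised endpoint text.
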